## 6. RATIONALE AND BACKGROUND

VynDAQel obtained the marketing authorization for the indication of “suppression of progression of peripheral neuropathy in transthyretin-type familial amyloid polyneuropathy” in September 2013. After an additional application for the indication of “transthyretin amyloid cardiomyopathy (hereinafter referred to as ATTR-CM)” was filed in November 2018, the approval for the additional application was obtained in March 2019.

VynDAQel is an orally available low molecular weight compound that binds to the thyroxine binding site of TTR and specifically stabilizes the TTR tetramers in plasma for both genetic variants and wild-type. This mechanism of action is expected to inhibit dissociation of the tetramers into monomers, which is a rate-limiting step in amyloid formation, suppress amyloid deposition in tissues such as the myocardium, and delay or deter the progression of ATTR-CM disease.

“VynDAQel Capsules Special Investigation - Investigation on patients with transthyretin amyloid cardiomyopathy -” (hereinafter referred to as this study) will be conducted to

*PFIZER CONFIDENTIAL*

*CT24-WI-JPN-GPSP01-RF09 7.0 Non-Interventional Study Protocol Template for Secondary Data Collection*

*Study 15-Sep-2022*

*Page 9 of 39*

comprehend information on the safety (e.g., onset status of adverse reactions), etc. of patients who are treated with Vyndaqel for the treatment of ATTR-CM.

Vynmac was approved for marketing in September 2021 for ATTR-CM because it demonstrated the same safety and tolerability as those of tafamidis meglumine 80 mg (20 mg x 4 capsules) containing the same physiologically active ingredient in patients with ATTR-CM. In this study, Vynmac is also investigated: when Vynmac is used during the observation period, observation will be also continued until the planned observation period is completed to comprehend information on the safety (e.g., onset status of adverse reactions), etc. of Vynmac.

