**8.2.4. Planned study period**

The planned period covered by this study is as follows.

Investigation period: March 2019 to September 2023 (From the start date of observation for the first subject to the end date of observation period for the last subject)

Registration period: March 2019 to March 2021 (From the start date of administration for the first subject to the start date of administration for the last subject)

However, CRFs may be collected when additional information needs to be collected.

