**8.2.5. Study procedures**

**8.2.5.1. Study method**

All patients surveillance system: This study will be conducted with all patients surveillance system that all patients will be registered until data are collected on a target number of patients.

This study investigates patients who used a marketed product of this drug after the approval for the indication for ATTR-CM is obtained at contract sites. This study targets patients who used this drug until contracts are concluded with sites requested to conduct the study and also

includes patients who used this drug after the conclusion of contracts (including retrospective patients).

When additional information needs to be collected, the investigator shall complete a CRF upon request of the Sponsor (Pfizer Japan Inc., hereinafter the same). When a patient, whose CRF is to be collected, is transferred to another hospital during the observation period, the investigator shall inform the Sponsor of the name of the transferred medical institution. The Sponsor shall conclude a contract to conduct this study with the transferred medical institution and conduct the study there.

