#### 8.6.9. All cases survey registration

1. The investigator will confirm whether all patients receiving this drug before 31 March 2021 are registered. The investigator should sign and affix a seal to the all-cases survey confirmation sheet and submit it to the site staff. E-mail etc. can be also used.
2. Any unregistered patients should be promptly registered.

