8.2.3.1.3. Details of adverse reactions

The number and proportion of patients with adverse reactions will be tabulated by SOC and PT for each of the following items:

- Seriousness [serious, non-serious]
- Number of days to onset [<26 weeks, \geq 26 weeks and <52 weeks, \geq 52 weeks and <78 weeks, \geq 78 weeks and <104 weeks, \geq 104 weeks and <130 weeks, \geq 130 weeks] (For the tabulation of incidence, the number of patients receiving at least one dose of this drug in each period category will be used as the denominator.)
- Action taken [suspended, dose reduced, dose increased, discontinued]

- Outcome [recovered/resolved, recovering/resolving, recovered/resolved with sequelae, not recovered/not resolved, fatal, unknown]

For outcomes, the number and proportion of patients with serious adverse reactions will be tabulated by SOC and PT.

If the same adverse reaction (of the same PT) occurs more than once in the same patient, it will be handled as follows in the tabulation of the number of patients with events:

- Seriousness: If both serious and non-serious events are reported, the event will be regarded as serious.
- Number of days to onset: Defined as the number of days to the first event.
- Action taken: If multiple types of actions were taken, one action will be adopted in the order of priority of discontinued, suspended or dose reduced, and other (none, dose increased).
- Outcome: The outcome of the last occurring event will be used.

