8.2.3.3. Exploratory analysis

For each of the factors specified in Section 5.4, the number and proportion of patients with at least one adverse reaction (incidence of any type of adverse reactions) will be tabulated, and for the incidence, the risk ratio among subgroups for each factor will be calculated as described in Section 8.1.3. However, after reconsidering the classification of a category with <10 patients, if calculation of a risk ratio is difficult, the

risk ratio to the category will not be calculated. In addition, unknown data will be excluded from the evaluation of risk ratios.

Serious adverse reactions and serious adverse events will also be analyzed in the same manner as above.

Adverse reactions will be tabulated by SOC and PT for each of the following subgroups:

- Liver impairment [absent, present]
- Renal impairment [absent, present]
- Age [<15 years, ≥15 to <65 years, ≥65 years]
- Pregnancy status [absent, present]
- NYHA functional classification [Class I, II, III, IV]

The onset status of adverse reactions will be evaluated for each product (Vyndaqel or Vynmac) during the treatment period until the first switching to Vynmac for Vyndaqel and during the treatment period after the first switching to Vynmac for Vynmac.

This drug is contraindicated to patients with a history of hypersensitivity to any of its ingredients. Because of limitations in evaluation in this study, no tabulation regarding contraindications will be performed. However, if hypersensitivity to any of its ingredients is reported as an adverse reaction, it will be presented in a listing.

Additional analyses may be performed as necessary. The exploratory analysis will be reported only when results giving important interpretation are obtained.

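### Vynmac periods can begin only about 5 months or more after Day 1, so the two by-product adverse-reaction results are not comparable and a difference cannot be attributed to product

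*SAP*

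**What the plan says.** Protocol 8.2.4 gives "Registration period: March 2019 to March 2021", running "to the start date of administration for the last subject". Protocol 8.6.9 asks investigators to "confirm whether all patients receiving this drug before 31 March 2021 are registered". Only marketed product counts. Protocol 8.2.5.1 states: "This study investigates patients who used a marketed product of this drug after the approval for the indication for ATTR-CM is obtained". Protocol 8.3 sets Day 1 for patients coming from clinical trials at their first marketed dose. Protocol 6 records that "Vynmac was approved for marketing in September 2021 for ATTR-CM".

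Protocol 8.2.6 sets 30 months of observation from Day 1, ending early at the first visit after discontinuation.

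Protocol 8.7 and SAP 8.2.3.3 both plan a by-product look at adverse reactions. In the SAP's words, onset is "evaluated for each product (Vyndaqel or Vynmac) during the treatment period until the first switching to Vynmac for Vyndaqel", with the period after the first switch assigned to Vynmac. Neither text gives a denominator, a rate, or an alignment on time since first dose. All other reaction analyses pool the two products.

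SAP 8.2.3.1.3 already tabulates pooled reactions in 26-week bands of time to onset, where "the number of patients receiving at least one dose of this drug in each period category will be used as the denominator".

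**The concern.** The two product periods sit one after the other in the same patients' treatment. If reactions depend on time since first dose, or if patients prone to react stop before they can switch, the two results will differ even when the products do not. Dividing by person-time does not cure this, because the periods cover different stages of treatment and different patients.

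Safety when Vynmac is used is a stated objective (Protocol 7, SAP 2.2), and this is the only analysis that separates the products. A reader shown two reaction figures will compare them. Depending on the shape of the reaction rate, the comparison could suggest a tolerability advantage that is not there, hide a real excess on Vynmac, or suggest an excess that is not there. The limitations in Protocol 8.9 mention neither the sequential periods nor selection into Vynmac.

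**Working it through.** The plan gives no figure for the by-product evaluation, so there is none to reproduce. The check has four steps.

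1. **Earliest possible Vynmac dose.** The last permitted start is 31 March 2021 (Protocol 8.2.4, 8.6.9). The approval day in September 2021 is not given. From 31 March to 1 September is 154 days (5.06 months), and to 30 September it is 183 days (6.01 months). It is longer if launch followed approval. At the other end, a patient who started in March 2019 finishes 30 months in about September 2021 and has almost no possible Vynmac time.

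2. **Who can be in the Vynmac period.** Observation ends at the first visit after discontinuation (Protocol 8.2.6). A patient who stopped for good before switching therefore contributes to Vyndaqel only.

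3. **Size of the distortion with identical products.** Assumptions: entry uniform over 25 months from 1 March 2019, everyone switches on 1 September 2021 (month 30), no dropout, and a reaction rate in months 0 to 6 that is *r* times the later rate.

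 - A patient entering at month *s* switches 30 − *s* months after Day 1. Mean Vynmac time is 12.5 of 30 months (41.7%), and mean Vyndaqel time is 17.5.
 - Mean Vyndaqel time in months 0 to 6 is 6 × 24/25 + 5.5 × 1/25 = 5.98, leaving 11.52 later. Vynmac time splits into 0.02 early and 12.48 later.
 - Rate ratio Vynmac:Vyndaqel = [(0.02*r* + 12.48)/12.5] / [(5.98*r* + 11.52)/17.5].
 - If everyone switches 6 months later, mean Vynmac time is 19²/50 = 7.22 months, all of it after month 6. Mean Vyndaqel time is 22.78, and the ratio is 22.78/(6*r* + 16.78).

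| *r* (early rate ÷ later rate) | Switch 1 Sept 2021 | Switch 6 months later |
|---|---|---|
| 0.5 | 1.21 | 1.15 |
| 1 | 1.00 | 1.00 |
| 2 | 0.75 | 0.79 |
| 3 | 0.60 | 0.65 |
| 5 | 0.43 | 0.49 |

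4. **Sensitivity by simulation, again with identical products.** Assumptions: entry from early-weighted to strongly late-weighted; either all patients switching at approval or 70% switching over the following 12 months; 1% discontinuing per month. Because the plan does not name a metric, both candidates are shown. The crude proportion uses switchers as the Vynmac denominator.

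| Assumed monthly reaction rate | Person-time ratio | Crude-proportion ratio |
|---|---|---|
| 3% to month 6, then 0.5% | 0.25 to 0.45 | 0.14 to 0.51 |
| 1% throughout | 1.00 | 0.30 to 1.85 |
| 0.4%, rising by 0.04 points a month | 1.47 to 1.89 | 0.45 to 3.38 |

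Crude proportions can differ widely in either direction even under a constant rate, purely because the two periods differ in length.

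**The case against.** The strongest reply is that no product comparison is planned. SAP 8.2.3.3 describes each product separately. Product is not among the SAP 5.4 factors that receive a risk ratio, and SAP 4 declares the study non-confirmatory, with no significance level or decision rule. The main safety evaluation is pooled. SAP 8.2.2.2 tabulates treatment period by product, so the sequence is visible, and the pooled 26-week bands would show whether reactions cluster early. Protocol 8.9 already concedes the lack of a control group and limited confounder data. All of this is correct and limits the weight of the point. It does not make the two figures comparable, and none of it tells the reader that they are not.

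Three stronger readings are tempting and are not supported:

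- A reader might infer that Vynmac is bound to look safer even if the products are identical. That needs reactions to cluster early, or in patients who then stop. The documents give no rate by time, entry distribution or switch share, and the tables above include ratios at and above 1.
- A reader might infer that patients reaching Vynmac had already tolerated Vyndaqel. They were only still under observation. SAP 8.2.2.2 provides for washout and for a change to Vynmac from a reduced Vyndaqel dose.
- A reader might treat Day 1 as first exposure for everyone. Protocol 8.3.1 includes patients from clinical trials and patients already treated for polyneuropathy, which weakens the early-versus-late contrast.

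The objection that banding spreads 300 patients thinly, and leaves selection within bands, also stands.

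**Conclusion.** The concern holds as a limit on interpretation. The documents' own dates establish that no surveyed patient could start on marketed Vynmac and that every Vynmac period begins at least about 5 months after Day 1. The Vyndaqel period takes essentially all initiation time and all patients who stopped before switching. A difference between the two by-product results therefore cannot be attributed to product.

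The dates are firm apart from the unstated approval day, which gives the range of 154 to 183 days. The size and direction of the distortion are not established: they rest entirely on the assumptions stated with the tables. This is a worthwhile, inexpensive improvement to an exploratory analysis that bears on a stated objective.

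**What to change.** In SAP 8.2.3.3:

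- Tabulate reactions by product within the 26-week bands of time since first dose used in SAP 8.2.3.1.3.
- Use person-time on that product within the band as the denominator. A patient who switches mid-band then contributes to each product only for the time on it. Carrying over the existing denominator, patients with at least one dose in the band, would count that patient in full under both products. Numerator and denominator should use the same product periods.
- Assign any Vynmac time before week 26 to Vynmac, but make no product comparison in that band. Because 26 weeks is 182 days and the earliest switch is at 154 days, a little such time is possible.
- Read the products together only in bands where both have meaningful exposure.

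In the report, state that no patient initiated treatment on Vynmac, that tolerability at initiation of Vynmac cannot be concluded from this survey, and that banding does not remove selection of who switched. Keep these statements even if counts prove too small for the banded table.

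The cost is SAP wording and one extra stratification. Product name and treatment period are already collected (Protocol 8.3.2), as is the date of each event (Protocol 8.3.8). The downside is sparse cells and wide intervals.

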##### 2. Method of analysis

- Analysis for safety evaluation

Events possibly related to this drug are considered as adverse drug reactions (ADRs). The number of patients with ADRs and the proportion  $[(\%): \text{number of patients with ADRs} / \text{number of patients included in the SAS}]$  will be calculated.

Based on the above method, important missing information and important potential risks will also be evaluated.

- Analysis for effectiveness evaluation

Time course of changes in the following items from the start of administration of this drug will be recognized.

- NYHA Functional Classification
- Cardiac biomarker values (NT-pro BNP, BNP, troponin I, and troponin T)

In addition, survival time analysis will be performed using survival information obtained up to 30 months after the start of administration.

- Subset analysis

The analysis by variant genotype and NYHA Functional Classification will be also performed for the above safety and effectiveness evaluations.

Also, the onset status of adverse reactions will be evaluated for each product (Vyndaqel or Vynmac) during the treatment period until the first switching to Vynmac for Vyndaqel and during the treatment period after the first switching to Vynmac for Vynmac.

Detailed methodology for summary and statistical analyses of data collected in this study will be documented in the SAP, which will be dated, filed and maintained by the Sponsor. The SAP may modify the plans outlined in the full protocol; any major modifications of primary endpoint definitions or their analyses would be reflected in a full protocol amendment.

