8.2.2.2. Administration status of this drug

For the safety analysis set, the following administration status of this drug will be tabulated:

- For a patient receiving Vynmac, the dose of Vyndaqel will be used in the tabulation of doses; 61 mg of Vynmac will be considered equivalent to 80 mg of Vyndaqel. Treatment period (continuous variable, unit = month)
 1. Treatment period for any product
 2. Treatment period with Vyndaqel before the initial switching to Vynmac
 3. Treatment period with Vynmac after the initial switching to Vynmac
- Treatment period (categorical variable, [<12 months, ≥12 to <24 months, ≥24 to <30 months, ≥30 months])
 1. Treatment period for any product
 2. Treatment period with Vyndaqel before the initial switching to Vynmac
 3. Treatment period with Vynmac after the initial switching to Vynmac
- Initial dose (categorical variable, [20 mg, 40 mg, 60 mg, 80 mg]; for an initial dose >80 mg, a subcategory of >80 mg will be used.)
- Number of doses per actual treatment period (excluding the washout period from the treatment period) (total number of doses/actual treatment period [days]) (continuous variable)
- Dose per actual treatment period (excluding the washout period from the treatment period) (total dose/actual treatment period [days]) (continuous variable)
- Number and proportion of patients with dose reductions*

*Including a dose change from Vynmac 61 mg to Vyndaqel ≤60 mg.
- Number and proportion of patients with dose increases**

** Including a dose change from Vyndaqel ≤60 mg to Vynmac 61 mg.

- Breakdown of reduced doses (categorical variable)

The frequency and proportion will be tabulated for each dose pattern (maximum dose \Rightarrow minimum dose) during the observation period* [80 mg \Rightarrow 60 mg, 80 mg \Rightarrow 40 mg, 80 mg \Rightarrow 20 mg, 60 mg \Rightarrow 40 mg, 60 mg \Rightarrow 20 mg, 40 mg \Rightarrow 20 mg, no change].

Treatment period is defined as the period from the first date of administration to the last date of confirmation of administration in this study, including washout period.

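### The by-product adverse-reaction summary splits time at the first switch only and has no exposure adjustment, so shorter time on Vynmac can look like a safety difference

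*SAP*

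**What the plan says.** Protocol 8.7 (Method of analysis, subset analysis) states that "the onset status of adverse reactions will be evaluated for each product (Vyndaqel or Vynmac) during the treatment period until the first switching". That window belongs to Vyndaqel; treatment time from the switch onward is assigned to Vynmac. SAP 8.2.3.3 repeats the rule. Its Vyndaqel window takes reactions "during the treatment period until the first switching to Vynmac for Vyndaqel". Its second window takes those that begin "during the treatment period after the first switching to Vynmac for Vynmac". Neither text says what happens when a patient goes back to Vyndaqel, and neither names a denominator, rate or risk ratio by product.

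SAP 8.2.2.2 does provide for a return. Its footnote on dose reductions reads "Including a dose change from Vynmac 61 mg to Vyndaqel ≤60 mg". The same section tabulates exposure by product, and its third item is "Treatment period with Vynmac after the initial switching to Vynmac". It defines treatment period in general as first to last confirmed administration, "including washout period".

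SAP 8.1.6 defines incidence per 100 person-years, but no analysis section cites it. Adjustment for exposure is requested only for the safety specifications (SAP 8.2.3.1.4), and that request points to the Kaplan-Meier section, 8.1.4.

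The dates come from the protocol: "Registration period: March 2019 to March 2021" (8.2.4), 30 months of observation (8.2.6), and "Vynmac was approved for marketing in September 2021 for ATTR-CM" (section 6).

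**The concern.** There are two separate weaknesses.

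The first is attribution. Read literally, everything after the first switch belongs to Vynmac until treatment ends. A reaction that begins after a return to Vyndaqel is then counted under Vynmac and cannot be counted under Vyndaqel. If the exposure item in 8.2.2.2 means Vynmac days only, the event window and the exposure window also differ.

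The second, and larger, is exposure. The two products are summarised side by side with no allowance for time at risk. Nobody in this cohort should have started on Vynmac, because registration had closed before it was approved. Its time comes from patients still on treatment at about month 6 or later, and on average it is the shorter part of their follow-up. The only adverse-reaction denominator that Protocol 8.7 defines is the whole safety analysis set, which would also include patients who never took Vynmac.

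Information on safety under Vynmac is a stated objective (Protocol 7, SAP 2.2), and this is the only by-product reaction analysis in the plan. A reader who sees a lower percentage for Vynmac could take a difference in follow-up for a difference in safety.

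**Working it through.** **The plan's own figure.** The documents give no calculation for the by-product summary. Their one design calculation (Protocol 8.5.2) concerns the pooled set: at least 10 cases among 300 at a true incidence of 5.88%. The exact binomial tail is P(X ≥ 10) = 0.984, so the stated figure of about 98% reproduces. It does not bear on the product split.

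**Time on each product.** Let s be the month of first administration, counted from March 2019. Registration gives s from 0 to 24, and Vynmac approval falls at month 30. With 30 months of follow-up per patient:

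- minimum Vyndaqel time = 30 − s, which ranges from 6 to 30 months;
- maximum Vynmac time = 30 − (30 − s) = s, which ranges from 0 to 24 months.

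With s uniform (assumption), the means are 18 and 12 months, a ratio of 1.5 to 1 if everyone switches at approval. Any delay widens it.

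**Crude proportions under equal hazards.** Let R be the 30-month risk (assumption; 5.88% is borrowed from Protocol 8.5.2 as a low value). The hazard is h = −ln(1 − R)/30 per month, and the expected proportion over t months is 1 − exp(−ht). For R = 20%, h = 0.00744:

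- 18 months: 1 − exp(−0.134) = 12.5%;
- 12 months: 1 − exp(−0.089) = 8.5%.

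Averaging over all start dates, with no dropout and with switchers as the Vynmac denominator, gives:

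| 30-month risk | Switching delay after approval | Crude Vyndaqel | Crude Vynmac | Ratio |
|---|---|---|---|---|
| 5.88% | 0 months | 3.56% | 2.39% | 0.67 |
| 20% | 0 months | 12.4% | 8.4% | 0.68 |
| 40% | 0 months | 25.9% | 17.9% | 0.69 |
| 5.88% | 6 months | 4.58% | 1.80% | 0.39 |
| 40% | 6 months | 32.3% | 13.9% | 0.43 |
| 5.88% | 12 months | 5.30% | 1.20% | 0.23 |
| 40% | 12 months | 36.7% | 9.6% | 0.26 |

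The true rate ratio is 1.00 in every row, and person-time rates would recover it.

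**Return to Vyndaqel.** Let f be the share of post-switch time spent back on Vyndaqel (not given; assumed 5% to 20%) and RR the true Vynmac/Vyndaqel rate ratio. The observed ratio is (1 − f) × RR + f:

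- RR = 1.0: observed 1.00 for any f;
- RR = 2.0: observed 1.95 (f = 5%) to 1.80 (f = 20%);
- RR = 0.5: observed 0.525 to 0.60.

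This effect is smaller than the exposure effect and always moves the ratio toward 1.

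**The case against.** The case for leaving the text alone has real force.

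- **No comparison is planned.** Product is not among the factors in SAP 5.4, and risk ratios are confined to those factors. A reader might infer that the plan formally compares Vynmac with Vyndaqel; it does not. This stands. The ratios above show what a reader could draw from two adjacent percentages.
- **The exposure item may already be right.** The words of item 3 in 8.2.2.2 can mean Vynmac days only, and the by-product sentence could be read the same way. That is possible, but 8.2.3.3 does not say so, and the two sections would still be worded differently.
- **Exposure by product is tabulated.** Number of patients times mean treatment period gives total time for each product, so a reader could form a rough rate. This stands in part: that total is not cut at the first event, includes washout, and may not match the event window.
- **Returns may matter little.** A reader might infer that returners are intolerant patients whose reactions are wrongly charged to Vynmac. The documents give neither the number of returns nor the reasons. A reaction that prompts a return begins on Vynmac and is correctly placed; only later ones are affected.
- **Nothing is lost for good.** A reader might also infer that attribution error and short follow-up work in opposite directions and cannot be untangled. The direction of the first depends on the true ratio. The second can be corrected, because drug name, treatment period and event date are all recorded (Protocol 8.3.2 and 8.3.8).
- **Shorter Vynmac time is an average.** In the model, 30 − s < s when s > 15, so (24 − 15)/24 = 37.5% of patients could have the longer period on Vynmac.
- **The stakes are limited.** The main safety analysis pools both products, the study is not confirmatory, and the Vynmac approval condition accepts data on either product.

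**Conclusion.** The point holds as a gap in an exploratory summary. As worded, reactions after a return to Vyndaqel fall to Vynmac, and no measure of time at risk is specified for either product.

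The unequal exposure is the part with a material size. Equal hazards would appear as a crude ratio of about 0.67 to 0.69 if all patients switched at approval, 0.39 to 0.43 with a 6-month delay, and 0.23 to 0.26 with a 12-month delay. These figures rest on uniform entry, a constant hazard, complete follow-up and an assumed 30-month risk of 5.88% to 40%. The switching pattern is not in the documents.

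The attribution error is secondary, and its size is unknown because the number of returns is not given.

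The documents do not support a claim that the main safety conclusions are at risk. Pooled results are untouched, so the change is worth making but is not a condition for the plan to stand.

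**What to change.** 1. In SAP 8.2.3.3, attribute each reaction to the product being taken at onset, using the dated administration record. State how an onset during washout is assigned, and show time and reactions after a return to Vyndaqel as a separate row.
2. Report reactions per 100 person-years by product with the method in SAP 8.1.6. That section now starts the clock at first administration, so PT must be redefined for this use, with Vynmac time starting at the switch.
3. Use the same product windows in the treatment-period items of SAP 8.2.2.2, and mirror the wording in Protocol 8.7.
4. Note in the report that Vynmac time comes from patients still on treatment and later in their course. Person-time corrects for length of exposure, not for that selection.

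The cost is a short text change and minor programming. No new data are needed, the analysis stays exploratory, and the pooled results do not change.

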5.4. Subgroups

Subgroup analyses of safety will be performed for the following patient characteristics and other factors. For the patient characteristics and other factors with those of specific categories underlined, a risk ratio will be calculated using each underlined category as the reference.

- Inpatient/outpatient status at the first prescription [inpatient, outpatient]
- *Severity of liver impairment [absent, mild, moderate, severe]
- Liver impairment [absent, present]
- Renal impairment [absent, present]
- Age [<15 years, ≥15 to <65 years, ≥65 years]
- *TTR genetic variant [wild-type, variant]
- NYHA functional classification [Class I/II, III/IV]
- NYHA functional classification [Class I, II, III, IV]
- Concomitant medication [absent, present]
- Non-drug therapy (device therapy) [absent, present]

- Complication [absent, present]
- Gender [male, female]
- Usage experience of this drug (administered this drug for the first time, transferred from clinical trials, transition from the treatment of ATTR-PN)

*Evaluation of the important missing information (safety in patients with severe liver impairment and patients with variants)

Subgroup analyses of efficacy will be performed for the following patient characteristics:

- TTR genetic variant [wild-type, variant]
- NYHA functional classification [Class I/II, III/IV]
- NYHA functional classification [Class I, II, III, IV]

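### As worded, SAP 8.2.3.3 and 8.2.4.4 make the reporting of planned subgroup and product analyses depend on their results

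*SAP*

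**What the plan says.** SAP 8.2.3.3 is headed Exploratory analysis and contains planned work:

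- Subgroup incidences and risk ratios: "For each of the factors specified in Section 5.4, the number and proportion of patients with at least one adverse reaction" is to be tabulated, with the same treatment for serious adverse reactions and serious adverse events.
- SOC/PT tables for five named subgroup factors, introduced by "Adverse reactions will be tabulated by SOC and PT for each of the following subgroups".
- The product analysis: "The onset status of adverse reactions will be evaluated for each product (Vyndaqel or Vynmac"), split at the first switch to Vynmac.

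The section then closes with two sentences in succession: "Additional analyses may be performed as necessary", followed by "The exploratory analysis will be reported only when results giving important interpretation are obtained". The same pair closes SAP 8.2.4.4, which holds the efficacy subgroup analyses by TTR variant and NYHA class.

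SAP 5.4 stars two of its safety factors, severity of liver impairment and TTR genetic variant, with the note "Evaluation of the important missing information (safety in patients with severe liver impairment and patients with variants"). Protocol 7.1 names the same two groups as important missing information.

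Protocol 8.7 states that "The analysis by variant genotype and NYHA Functional Classification will be also performed for the above safety and effectiveness evaluations". It also plans an evaluation of the important missing information and of adverse reactions for each product. None of these statements depends on what the results show.

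**The concern.** Taken literally, the closing sentence lets the sponsor look at a planned subgroup or product result and then decide whether it goes into the report. No criterion for importance is given, and SAP 4.1 adds that a screening threshold may be chosen afterwards.

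This matters most for the two missing-information groups and for Vynmac. For these, an unremarkable result is useful: it helps to answer the open safety question. A rule that favours striking results could leave such a result out. Readers would also be unable to tell whether a missing subgroup table means that nothing was found, that too few patients were available, or that the analysis was not done.

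**Working it through.** The plan states no figure on this point, so the check sets the texts side by side.

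**1. What the closing sentence refers to.** Two readings are possible.
- Narrow: it qualifies only the extra analyses of the sentence just before it.
- Broad: it qualifies the whole section. Its subject, the exploratory analysis in the singular with the definite article, repeats the section heading. The preceding sentence speaks of additional analyses in the plural.

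The wording fits the broad reading better, and nothing in the text excludes it.

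**2. What falls under the broad reading.**
- Safety (8.2.3.3): the 13 factors listed in 5.4, each for three outcomes (any adverse reaction, serious adverse reactions, serious adverse events); SOC/PT tables for five factors; the product analysis.
- Efficacy (8.2.4.4): TTR variant, and NYHA in two groupings, applied to the 8.2.4 analyses. The MMRM and the figures are already excluded from subgroup analysis by 8.2.4.2.

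**3. Whether another section guarantees reporting.**
- SAP Section 3 says that every specified analysis is carried out at the final analysis. It does not mention reporting.
- SAP 8.2.3.1.4 tabulates the safety specifications of Section 6.1, but 6.1 names only the important potential risks. The missing-information groups are not named there.
- Protocol 8.7 sets no condition on the result, but it too speaks of performing and evaluating.

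**4. What would remain if 8.2.3.3 and 8.2.4.4 went unreported.**

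| Result | Available elsewhere? |
|---|---|
| Adverse-reaction proportion, variant patients | Yes, crudely: patients in the Section 9 variant listing divided by the variant count in 8.2.2.1 |
| Adverse-reaction proportion, severe liver impairment | Yes, crudely: patients in the Section 9 severe-liver listing divided by the severe count in 8.2.2.1 |
| Variant versus wild-type comparison | Not reliably: wild-type reactions = all − variant − unknown genotype, and no listing isolates the unknown group |
| Comparison across liver-impairment severity | No: only the severe category has its own listing |
| Serious adverse events by genotype or liver severity | No planned table. Section 9 has a general listing, but the SAP does not say that it shows these characteristics |
| Adverse reactions by product | No: 8.2.2.2 gives treatment periods by product, not reactions |
| Survival by genotype and NYHA | No planned estimate outside 8.2.4.4 |
| Biomarkers by genotype and NYHA | Partly: spaghetti plots distinguished by both factors in 8.2.4.2 |

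**5. Direction of the effect.** If reporting is selected on results, the reported set tends towards the more extreme ones. That follows from the selection itself and needs no assumption about the true effects.

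**The case against.** The strongest reply is that the narrow reading is the intended one. The sentence comes straight after the one on additional analyses. The same section firmly promises a listing if hypersensitivity to an ingredient is reported as an adverse reaction, which would sit oddly under a rule that makes the whole section optional. SAP version 6.0 amended 8.2.3.3 specifically to name the SOC/PT subgroups, which is a strange effort for tables that may never appear. This is good evidence of intent, and it stands. It does not change what the sentence says, and someone preparing the report could follow either reading in good faith.

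A second reply is that the missing-information groups do not disappear. That also stands. A reader might infer that the listings lack denominators, so that nothing could be said about these patients. The documents do not support this: 8.2.2.1 tabulates TTR genotype and liver-impairment severity whatever the outcome.

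A reader might also multiply factors by outcomes, take 5% of the product, and call that the expected number of chance findings that would be reported. The documents do not support that either. Risk ratios are planned only for factors with an underlined reference category, and the underlining cannot be seen in the available text. They may also be dropped for categories with fewer than 10 patients. The comparisons overlap heavily: NYHA and liver impairment each appear twice, and serious adverse reactions are contained in both other outcomes. Finally, the rule's trigger is importance of interpretation, not a confidence interval that excludes 1.

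The re-examination and periodic-report forms required by Section 9 may carry some of these results, but their contents are not in the documents.

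**Conclusion.** The point holds as a defect of wording with a real consequence if the sentence is applied literally. Planned analyses that serve protocol 8.7 become reportable at discretion after the results are seen. Its reach is the 13 safety factors for three outcomes, the SOC/PT subgroup tables, the product analysis, and the genotype and NYHA efficacy subgroups. Its practical weight falls on the planned comparisons, the serious-adverse-event incidences by subgroup and the product analysis, because crude adverse-reaction proportions for variant and severe-liver patients can be rebuilt. No numerical bias is claimed. The conclusion assumes only that a report writer could apply the sentence as it stands.

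Two stronger inferences should be resisted. One is that the SAP breaches the protocol. Protocol 8.7 commits to doing these analyses, the SAP also commits to doing them, and the protocol allows the SAP to modify outlined plans. The gap is in reporting. The other is that leaving TTR variant and liver-impairment severity out of the SOC/PT subgroup list, where the liver entry is only "Liver impairment [absent, present"], contradicts the protocol. It does not: protocol 8.7 defines the safety method as counts and proportions of patients with adverse drug reactions, and nowhere promises SOC/PT tables by genotype or severity.

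**What to change.** In both 8.2.3.3 and 8.2.4.4, restrict the closing sentence to additional analyses that the plan does not specify. Add one sentence stating that all Section 5.4 subgroup results, for safety and efficacy, and the Vyndaqel/Vynmac analysis are reported whatever they show. Where a risk ratio is not calculated under the existing small-category rule, the report should say so.

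The cost is a short SAP wording change. No new data or analyses are needed, since Section 3 already requires these analyses to be run at the final analysis. Adding TTR variant and severity of liver impairment to the SOC/PT subgroup list would be a useful option at the cost of two tables, but it is not a correction.
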